3.13.4. Other Secondary

Unless otherwise specified, other secondary analyses will be guided by the treatment policy strategy using all randomized population. Missing data will not be imputed unless otherwise specified. The other secondary analyses can be seen in Table GPID.3.4.

Table GPID.3.4. Other Secondary

Objectives	Endpoints	Analytical Approaches
Hierarchical	A hierarchical composite of the	The win ratio (Pocock et al. 2012) will be
composite	following:	reported as the measure of treatment effect
_	time to all-cause mortality	based on the principle that each participant is
	through the end of follow-up	compared with every other participant within
	occurrence of HF events	each stratum in a pair-wise manner that
	through end of follow-up,	proceeds in a hierarchical fashion.
	where HF events are as defined	Participants will be stratified according to HF
	in Section 1.1	decompensation within 12 months of
	 number of HF events 	screening (Y/N), diagnosed T2DM (Y/N), and
	• time to first HF events	baseline BMI group (<35 , ≥35 kg/m ²),
	 change from baseline in 	yielding 8 stratification pools. The variance of
	KCCQ-CSS category at Week	win ratio will be calculated by the asymptotic
	52, and	normal U statistic approach (Dong et al.
	Change from baseline in the	2018).
	6MWD category at Week 52.	Missing KCCQ-CSS and 6MWD will be
	The categories for change from baseline	imputed as described in Section 3.13.1.3.
	in the KCCQ-CSS are:	
	1. ≥10-point worsening	
	2. ≥5- but <10-point worsening	
	3. No change (<5-point change)	
	4. ≥5- but <10-point	
	improvement	
	5. ≥10- but <15-point	
	improvement, and	
	6. \geq 15-point improvement.	
	The categories for change from baseline	
	in the 6MWD are:	
	1. ≥30% worsening	
	2. ≥20% and <30% worsening	
	3. \geq 10% and \leq 20% worsening	
	4. no change (<10% change)	
	5. $\geq 10\%$ and $\leq 20\%$ improvement	
	6. $\geq 20\%$ and $\leq 30\%$ improvement,	
	and	
	7. ≥30% improvement.	
Clinical outcome	Time to all-cause death	The time from randomization to the first
events of HF	Time to first occurrence of HF	occurrence of any component of the
	events or all-cause death	composite endpoint will be analyzed by a Cox
	• Time to recurrent events of HF	proportional hazards model similar to the
	events and all-cause death	model described in Section 3.13.1.2.1.2.
	Time to first occurrence of HF	
	events	Time to recurrent event analyses will be
	Time to recurrent events of HF	performed using a LWYY as specified in
	events	Section 3.13.1.5. Similar 30-day spacing rule
		will be applied as described in
		Section 3.13.1.5.

Objectives	Endpoints	Analytical Approaches
NYHA Class	Proportion of participants with NYHA Class improvement at Week 52.	Logistic regression analysis will be conducted including treatment, stratification factors, and baseline NYHA Class in the model.
Weight loss	Proportion of participants attaining \geq 5%, \geq 10%, \geq 15% and \geq 20% in body weight reduction change at Week 52.	Logistic regression analysis will be conducted including treatment, stratification factors excluding baseline BMI group (<35, ≥35 kg/m²), and the continuous covariate of baseline body weight value in the model. Missing body weight measurements at Week 52 will be imputed using a retrieved dropout approach (as described in Section 3.13.2.2) through multiple imputation.
Exercise capacity	 Change from baseline to Week 24 in 6MWD Proportion of participants attaining 6MWD MWPC threshold at Week 52 Proportion of participants attaining ≥10 meters, ≥20 meters, and ≥30 meters 6MWD change at Week 52 	A similar nonparametric approach to the one described in Section 3.13.1.1.2 will be conducted. Logistic regression analysis will be conducted including treatment, stratification factors, and baseline 6MWD in the model. The MWPC threshold at Week 52 is decided in analysis conducted separately guided by the PAP. Missing 6MWD measurements at Week 52 will be imputed through multiple imputation, as specified in Section 3.13.1.3.
Patient-reported symptoms and physical limitations	 Change from baseline to Week 24 in KCCQ-CSS Proportion of participants attaining KCCQ-CSS MWPC threshold at Week 52 Proportion of participants attaining ≥5 meters, ≥10 meters, and ≥15 points KCCQ-CSS change at Week 52 	A similar nonparametric approach to the one described in Section 3.13.1.1.2 will be conducted. Logistic regression analysis will be conducted including treatment, stratification factors, and baseline 6MWD in the model. The MWPC threshold at Week 52 is decided in analysis conducted separately guided by the PAP. Missing KCCQ-CSS measurements at Week 52 will be imputed through multiple imputation as specified in Section 3.13.1.3.

Abbreviations: 6MWD = 6-minute walk test distance; BMI = body mass index; HF = heart failure;

KCCQ-CSS = Kansas City Cardiomyopathy Questionnaire – Clinical Summary Score; LWYY = Lin-Wei-Yang-Ying; MWPC = meaningful within-patient change; NYHA = New York Heart Association; PAP = psychometric analysis plan; T2DM = type 2 diabetes mellitus.

Note: MWPC threshold at Week 52 for KCCQ-CSS is 20; MWPC threshold at Week 52 for 6MWD is 25 meters.

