2.3. Benefit/Risk Assessment

More detailed information about the known and expected benefits and risks and reasonably expected AEs of tirzepatide may be found in the Investigator's Brochure.

3. Objectives and Endpoints

Objectives	Endpoints
Primary	
To demonstrate that a maximally tolerated tirzepatide dose up to 15 mg administered SC QW is superior to placebo to improve patient-reported symptoms and physical limitations in participants with HFpEF and obesity	Change from baseline to Week 52 in the KCCQ-CSS
To demonstrate that a maximally tolerated tirzepatide dose up to 15 mg administered SC QW is superior to placebo based on the composite HF outcome endpoint in participants with HFpEF and obesity	Occurrence of the composite endpoint of CV death and/or HF events over time
Key Secondary (multiplicity controlled)	
Exercise capacity	Change from baseline to Week 52 in 6MWD
Long-term weight loss	Percent change from baseline to Week 52 in body weight
Evaluation of change in inflammation	Change from baseline to Week 52 in hsCRP
Other Secondary	
Hierarchical composite assessed by win ratio	 A hierarchical composite of the following: Time to all-cause mortality through the end of the study Occurrence of heart failure (HF) events through end of the study, where HF events are defined as worsening heart failure with intensification of diuretics (oral or IV) during a hospitalization, urgent care visit or outpatient visit (adjudicated) number of HF events time to first HF events Change from baseline in KCCQ-CSS category at Week 52

	4. Change from baseline in the 6-minute walk test distance (6MWD) category at Week 52
	The categories for change from baseline in the KCCQ-CSS are:
	 ≥10-point worsening ≥5- but <10-point worsening No change (<5-point change) ≥5- but <10-point improvement ≥10- but <15-point improvement ≥15-point improvement
	The categories for change from baseline in the 6MWD are:
	 ≥30% worsening ≥20% and <30% worsening ≥10% and <20% worsening No change (<10% change) ≥10% and <20% improvement ≥20% and <30% improvement ≥30% improvement.
Clinical outcome events of HF	Time to all-cause death
	Time to first occurrence of HF events or all-cause death
	• Time to recurrent events of HF events and all-cause death
	• Time to first occurrence of HF events
	• Time to recurrent events of HF events
New York Heart Association (NYHA) Class	Proportion of participants with NYHA Class change at Week 52
Exercise capacity	Change from baseline to Week 24 in 6MWD

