4.1. Overall Design

Study GPID is a randomized, outpatient, multicenter, international, placebo-controlled, double-blinded, parallel-arm, Phase 3 study with 2 study periods. The study is designed to evaluate the efficacy and safety of SC QW tirzepatide, MTD up to 15 mg, compared to placebo, in participants with HFpEF and obesity.

Two intervention groups will be studied:

- Tirzepatide MTD up to 15 mg SC QW
- Placebo

The study will compare treatment with tirzepatide and treatment with placebo. Assignment to tirzepatide or placebo groups will be randomly allocated in a 1:1 ratio.

The starting dose of tirzepatide or placebo is 2.5 mg QW, which is to be escalated at 4-week intervals to a maximum of 15 mg QW or to the highest maintenance dose tolerated by the participant (see Section 6).

The study will consist of 2 periods:

- Study Period 1: screening period, lasting no more than 12 weeks.
- Study Period 2: treatment period, with a 20-week escalation followed by at least a 32-week maintenance period.

The study will continue until approximately 52 weeks after the last participant is randomized. The maximum duration of an individual's participation is estimated to be 120 weeks and will depend on duration of study enrollment.

Participant Visit Scheme

Study participants will undergo screening assessments and procedures, randomization, and double-blinded treatment with tirzepatide or placebo. Assessments and procedures to be conducted in each treatment period are described in the SoA (Section 1.3) and in Study Assessments and Procedures (Section 8).

Screening

Screening procedures will be performed at Visit 1. Visit 1 procedures may be conducted over more than 1 day as long as all activities are completed within the allowable visit tolerance for each visit. The duration of Visit 1 is anticipated to be <6 weeks but may be longer. Visit 1 should no more than 12 weeks from date of informed consent.

At Visit 1, two 6MWTs will be conducted. The investigator must ensure that the participant is recovered from completion of the first 6MWT prior to conducting the second 6MWT (at least 1 hour between each test). The screening 6MWTs may be conducted over more than 1 day.

Randomization

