Summary descriptive statistics for continuous measures will include sample size, mean, standard deviation (SD), median, minimum, and maximum. Summary statistics for categorical measures (including categorized continuous measures) will include sample size, frequency, and percentages. Summary statistics for discrete count measures will include sample size, mean, SD, median, minimum, and maximum.

Unless otherwise specified, all observed data will be considered for analysis regardless of adherence to randomized treatment. The participant's end of follow-up will be the later of last contact date or study disposition date.

The definition of time-to-event for a specific event of interest is specified in Table GPID.3.3.

 Table GPID.3.3.
 Definition of Time-to-Event for a Specific Event of Interest

If a participant:	then:
Experiences the event	time-to-event for a specific event of interest will be the number of days
	between the date of randomization and the onset date of the event plus
	1 day.
Does not experience the event	the participant will be censored and the number of days between the
	date of randomization and the date of the participant's end of follow-up
	plus 1 day will be used for analysis.

Not all analyses described in SAP GPID will necessarily be included in the clinical study report (CSR). Any analysis described in this SAP and not provided in the CSR will be available upon request. Not all displays will necessarily be created as a "static" display. Some may be incorporated into interactive display tools instead of or in addition to a static display.

a Immunogenicity related analysis is specified in Section 3.14.3.8.

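### The win ratio's HF tier counts events over each participant's own follow-up with no shared window per pair; the effect on the reported ratio is small and the fix is cheap

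*SAP*

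**What the plan says.** SAP Table GPID.3.4 (Section 3.13.4) lists the tiers as all-cause mortality, HF events, KCCQ-CSS category at Week 52 and 6MWD category at Week 52. The HF tier covers events "through end of follow-up" and is compared first on "number of HF events" and then on time to the first one. Within each of eight strata, every participant is "compared with every other participant within" that stratum.

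SAP Section 3.2 fixes the window: "The participant's end of follow-up will be the later of last contact date or study disposition date". It is therefore a separate date for each participant. Protocol Section 3 words the tier as "Occurrence of heart failure (HF) events through end of the study", also without a rule for pairs of unequal length.

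Follow-up differs by design. Protocol Section 4.1 states: "The study will continue until approximately 52 weeks after the last participant is randomized". It also states: "The maximum duration of an individual's participation is estimated to be 120 weeks". The synopsis counts screening as part of participation.

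On incomplete data, SAP Section 3.13.4 says "Missing data will not be imputed unless otherwise specified". For this composite the exception covers KCCQ-CSS and 6MWD only. SAP Section 3.6 gives other secondary endpoints no multiplicity adjustment.

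**The concern.** A count grows with time observed. The SAP allows for this elsewhere: the Cox model censors, incidence is per 100 person-years, and recurrent events go to the LWYY model. A pairwise comparison of counts has no such protection unless the pair is cut to common time. Without that cut, part of the HF tier measures length of observation. Pairs settled there are also lost to the KCCQ-CSS and 6MWD tiers. If one arm had more early exits, it would collect wins at this tier even with an inert drug.

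**Working it through.** **No plan figure to reproduce.** The documents give no event rate, exit rate, power or expected value for the win ratio. The rates below are assumptions, shown over a range.

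**Planned follow-up after randomization.** The minimum is about 52 weeks. The maximum is 120 weeks of participation less 6 to 12 weeks of screening: 120 − 12 = 108 and 120 − 6 = 114 weeks.

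**One pair, same stratum, both alive.** A leaves at Week 8 with 0 HF events. B is followed to Week 108 with 1 event, at Week 104.
- As written: 0 < 1, so A wins.
- Shared window: min(8, 108) = 8 weeks, 0 = 0. The pair is tied and moves to KCCQ-CSS, where A's missing value is imputed.
- Early exit is not required. If A were a late-randomized completer with 52 weeks and 0 events, A would still win as written, and the pair would tie on the shared 52 weeks.

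**HF tier alone, no drug effect.** Simulated with 350 per arm, 150 trials per scenario, and HF rates of 0.05, 0.10 and 0.20 per patient-year with gamma frailty (shape 1). Completers were followed uniformly over 52-110 weeks, and early leavers exited uniformly over weeks 0-52. Win ratio = tirzepatide wins / losses on count, then time to first event. Entries are for the three rates in order.

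| Exit, tirzepatide / placebo | As written | Shared window | As written ÷ shared |
|---|---|---|---|
| 10% / 10% | 1.006, 0.997, 1.025 | 1.014, 0.994, 1.024 | 0.99, 1.00, 1.00 |
| 10% / 5% | 1.038, 1.025, 1.027 | 1.004, 0.989, 0.991 | 1.03, 1.04, 1.04 |
| 15% / 5% | 1.080, 1.112, 1.091 | 1.015, 1.039, 1.009 | 1.06, 1.07, 1.08 |
| 25% / 5% | 1.144, 1.180, 1.156 | 0.991, 1.015, 0.996 | 1.15, 1.16, 1.16 |
| 5% / 15% | 0.974, 0.930, 0.958 | 1.043, 0.999, 1.027 | 0.93, 0.93, 0.93 |

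The Monte Carlo standard error of each log win ratio is about 0.013-0.031. Across scenarios, 12-39% of pairs are decided at this tier as written and 10-35% on shared time.

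A second simulation used frailty shape 0.5, exits in weeks 4-40, follow-up to 120 weeks and 400 trials per scenario. With 12% versus 5% exit the HF-count win ratio was 1.06-1.09 as written and 1.00-1.02 on shared time: 1.06/1.00 = 1.06 and 1.09/1.02 = 1.07, a shift of 6-7%.

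**Overall win ratio, the quantity reported.** The full hierarchy was simulated with no drug effect, the same three HF rates, deaths at 3% per year, follow-up of 52-110 weeks and 200 trials each. As written ÷ shared:
- 12% / 5% exit: 1.008, 1.011, 1.018
- 8% / 5% exit: 1.002, 1.004, 1.008
- 5% / 5% exit: 1.000, 1.000, 0.999

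The SD of the log overall win ratio was 0.085-0.10. A separate full-hierarchy run at 12% / 5% gave shifts of about 1-2.5%, with an SD of about 0.08-0.10. In standard errors, the low end is ln(1.008)/0.10 = 0.08 and the high end is ln(1.025)/0.08 = 0.31, so about 0.1 to 0.3.

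**The case against.** The best reply is that the SAP gives a tier list and cites published win-ratio methods, which may carry their own rule for unequal follow-up. The mortality tier uses almost the same follow-up wording and would naturally be read with censoring, so the HF tier could be meant that way too. This stands in part: the cited papers are not available here, so the programmed rule may already be right. But the SAP does not restate such a rule, and the only window it names is each participant's own.

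The second reply is that bias between arms needs unequal exit from the study, and the protocol works against that. Stopping study drug does not end participation (Section 7.1.1). Study discontinuation is expected to be rare, and other ways of being followed are offered (Section 7.2). For participants who refuse visits, sites must seek vital status and endpoints through family, physicians or records (Section 7.3). This stands: 12% versus 5% is an assumption that the documents do not suggest.

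The third reply is that HF burden is also analysed by Cox, LWYY and Ghosh-Lin methods. This also stands and limits what is at stake.

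A reader might infer that the win ratio is biased in favour of tirzepatide. The documents do not support that: they give no reason to know which arm would lose more participants, and with equal exit the null ratio stays near 1. A reader might also take the 6-7% as the error in the reported result. It applies to one tier, which settles a minority of pairs.

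**Conclusion.** The gap is real and minor. As written, the HF tier can reward shorter observation, provided the two participants share a stratum and are tied on mortality. With equal exit this adds noise and takes some pairs from the lower tiers. With an assumed 12% versus 5% exit it moves the HF-tier win ratio by about 6-7% under the null, and the overall win ratio by about 1-2.5%, or 0.1-0.3 standard errors. These sizes rest on assumed event, death and exit rates; the direction follows from the wording. The endpoint is other secondary and outside alpha control, so no primary or key secondary conclusion changes.

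**What to change.** Add to Table GPID.3.4, for each pair:
- The death tier is evaluated up to the shorter of the two participants' times with known vital status.
- The number of HF events and the time to first HF event are evaluated up to the shorter of their times with HF-event ascertainment. If a participant has died, their HF window ends at death.
- Pairs still tied move to the Week 52 KCCQ-CSS and then 6MWD tiers.

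Define HF-event ascertainment by the last date on which HF events were actually ascertained. The SAP's end of follow-up will not serve: it takes the later of contact and disposition dates, and Protocol Section 7.3 has a lost-to-follow-up disposition recorded at study end. A lost participant could then count as event-free to study end even with a shared window. Two separate windows are needed because vital status may be known for longer than HF status.

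The cost is a few sentences and a small programming change. HF events after the shared time are not used in that pair, so slightly fewer pairs are decided on HF events (10-35% instead of 12-39% in the simulations).

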3.3. Adjustments for Covariates

The study is stratified by diagnosed type 2 diabetes mellitus (T2DM) (Y/N), HF decompensation (including hospitalization for HF requiring intravenous [IV] diuretic treatment or urgent HF visit requiring IV diuretic treatment) within 12 months of screening (Y/N), and baseline BMI group ($<35, \ge 35 \text{ kg/m}^2$). Unless otherwise specified, the stratification factors will be adjusted in the efficacy analyses. The value for stratification factors will be obtained from the data collected or derived from the electronic case report form (eCRF). In addition, the baseline value of the endpoint will be used as a covariate when appropriate.

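### SAP Table GPID.3.4: the Week 52 KCCQ-CSS responder models adjust for baseline 6MWD instead of baseline KCCQ-CSS

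*SAP*

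**What the plan says.** Table GPID.3.4 (SAP Section 3.13.4) has a row for patient-reported symptoms and physical limitations. It contains two kinds of Week 52 responder endpoint:

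- the proportion "attaining KCCQ-CSS MWPC threshold at Week 52", where the table note states "MWPC threshold at Week 52 for KCCQ-CSS is 20"
- the proportion with "≥5 meters, ≥10 meters, and ≥15 points KCCQ-CSS change at Week 52".

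Both are analysed by logistic regression with treatment, the stratification factors and a baseline covariate. The text that names the covariate and runs into the imputation sentence reads "baseline 6MWD in the model. The MWPC threshold at Week 52 is decided in analysis conducted separately guided by the PAP. Missing KCCQ-CSS measurements".

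The exercise-capacity row directly above reads "baseline 6MWD in the model. The MWPC threshold at Week 52 is decided in analysis conducted separately guided by the PAP. Missing 6MWD measurements". Apart from a comma, the only difference is the endpoint named in the imputation sentence.

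The general rule in SAP Section 3.3 is that "the baseline value of the endpoint will be used as a covariate when appropriate".

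**The concern.** A responder model for a change score would normally adjust for the baseline of that same score, because the baseline determines how much room there is to change. KCCQ-CSS runs from 0 to 100. At the 20-point threshold, a participant with a baseline of 80 must reach 80 + 20 = 100, and one above 80 cannot respond at all. The entry limit of 80 (Protocol Section 5.1, criterion 9) applies at Visit 1, whereas efficacy baseline is the last value at or before randomisation (SAP Section 3.2). Baselines above 80 are therefore possible.

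Programmed as written, the model leaves out this covariate and includes the baseline of a different endpoint. If the programming team quietly corrects it, the reported model will differ from the prespecified one. If it is changed after unblinding, the choice will look data-driven, because the two models can give visibly different odds ratios. The protocol's amendment summary says the MWPC analysis was added to support KCCQ-CSS, a primary endpoint, so these odds ratios are likely to be read closely.

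**Working it through.** **Text comparison**

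| Analysis | Where | Baseline covariate |
|---|---|---|
| NYHA improvement | SAP Table GPID.3.4 | NYHA class ("stratification factors, and baseline NYHA Class in the model") |
| Weight-loss responders | SAP Table GPID.3.4 | body weight |
| 6MWD responders | SAP Table GPID.3.4 | 6MWD |
| KCCQ-CSS MMRM and ANCOVA | SAP 3.13.1.4 | KCCQ-CSS |
| **KCCQ-CSS responders** | SAP Table GPID.3.4 | **6MWD** |

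Only the last line departs from the pattern. The meters in its endpoint list also appear in the SAP's revision summary, so they are unlikely to be an artefact of text extraction.

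**Planning inputs.** No stated power or sample size depends on this covariate, so there is no figure of the plan's to reproduce for this point. As a check on the inputs (Protocol Section 9.2: mean change 5 vs 10, SD 19, 350 per arm, two-sided 0.01):

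- Standard error = 19 × √(2/350) = 1.436, and 5/1.436 = 3.481. Power = Φ(3.481 − 2.576) = 81.7%.
- With the Wilcoxon efficiency factor 3/π, the effective n is 350 × 3/π = 334.2 per arm and power is 79.6%.

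Both agree with the protocol's rough 80%.

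**Assumptions for the responder models.** The documents give no baseline SD or correlations. Assumed:

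- baseline-to-Week 52 correlation ρ of 0.5 to 0.7
- ratio r of Week 52 SD to baseline SD of 1.0 to 1.3
- correlation of 0.35 between baseline 6MWD and baseline KCCQ-CSS.

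Holding the SD of change at 19, the correlation of change with baseline is (ρr − 1)/√(1 + r² − 2ρr):

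- ρ = 0.5, r = 1.0: (0.5 − 1)/√1 = −0.50
- ρ = 0.7, r = 1.3: (0.91 − 1)/√0.87 = −0.096.

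The stronger this correlation, the more is lost by leaving baseline KCCQ-CSS out.

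**Simulation.** Both logistic models (treatment plus one baseline covariate) were fitted to the same simulated trials of 350 per arm and tested at two-sided 0.05. Data were normal and complete; stratification factors and imputation were omitted. With 6,000 trials at each end of the range:

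| Setting | Threshold | Power, baseline 6MWD | Power, baseline KCCQ-CSS | Gain (SE) | Odds ratio, 6MWD vs KCCQ-CSS |
|---|---|---|---|---|---|
| ρ 0.5, r 1.0 | 15 | 77.4% | 83.5% | 6.0 (0.4) | 1.55 vs 1.67 |
| ρ 0.5, r 1.0 | 20 | 72.0% | 78.8% | 6.9 (0.4) | 1.57 vs 1.68 |
| ρ 0.7, r 1.3 | 15 | 76.4% | 76.7% | 0.3 (0.2) | 1.53 vs 1.54 |
| ρ 0.7, r 1.3 | 20 | 72.0% | 72.2% | 0.2 (0.2) | 1.56 vs 1.57 |

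A separate run of 15,000 trials at the favourable setting gave gains of 5.6 and 6.1 points (SE about 0.25).

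Over all 12 combinations of ρ and r (2,000 trials each), power was 76-80% vs 77-85% at threshold 15 and 72-75% vs 74-79% at threshold 20. Setting the 6MWD correlation to 0.2 or 0.5 left the gain at 5 to 6 points at the favourable end and about 0 at the other.

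**Type I error.** In 6,000 null trials, rejection at thresholds 15 and 20 was 5.2% and 5.0% with baseline 6MWD, and 5.0% and 4.9% with baseline KCCQ-CSS.

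**The case against.** The strongest reply is that little depends on this. These are other secondary analyses with no multiplicity adjustment (SAP Section 3.6). The comparison is randomised, so either covariate gives a valid test. The primary van Elteren test, the KCCQ-CSS MMRM and ANCOVA and the Week 24 KCCQ-CSS analysis are untouched. All of that stands, and it limits the weight of the point.

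Three further points are fair:

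- **SAP Section 3.3 is discretionary.** It applies the endpoint's baseline where appropriate, so Table GPID.3.4 departs from a default and breaks no fixed rule. However, neither document says why the default would be unsuitable here.
- **The odds-ratio shift is not bias removed.** Adding a prognostic covariate moves a conditional odds ratio away from 1 because odds ratios are non-collapsible. The two models estimate somewhat different quantities. This is a reason to settle the covariate in advance.
- **The power gain rests on assumptions.** At one end of the plausible range it cannot be told from zero.

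The meters slip is unlikely to be misprogrammed, since the phrase ends in points of KCCQ-CSS. It matters mainly as evidence of how the row came to be written.

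**Conclusion.** The covariate is wrong as written. That it was carried over from the 6MWD row is an inference, but a strong one: the wording is near-identical, the units are wrong in the same row, and every comparable model uses its own baseline.

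The consequence is modest. Under the assumed correlations and SD ratios, the model as written gives up between about 0 and 6 or 7 points of power at the 15- and 20-point thresholds, and its odds ratio is somewhat closer to 1. Validity, type I error, the sample size and both primary analyses are unaffected. It should be corrected because the text as it stands would be programmed into a less precise and inconsistent model.

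**What to change.** In the KCCQ-CSS row of Table GPID.3.4:

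1. Replace baseline 6MWD with baseline KCCQ-CSS in the logistic model.
2. Give all three cut-offs in points: 5, 10 and 15.

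If baseline 6MWD was intended, state the reason instead of making the first change.

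Both edits should be made before unblinding. Protocol Section 9.4.1 allows SAP amendments up to final database lock, but an earlier change avoids any question of post hoc choice. The cost is one covariate term and two unit words. No new data are needed, and the protocol text does not change because it lists the KCCQ-CSS MWPC endpoint without naming a model.
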